Full title:

A Multicenter Randomized Controlled Trial Assessing the Efficacy of Antimicrobial Prophylaxis for Extracorporeal Shock Wave Lithotripsy on Reducing Urinary Tract Infection

Brief Title:

Antibiotic Prophylaxis Before Shock Wave Lithotripsy (APPEAL)

1. Objectives & Specific Aims

The lifetime risk of developing nephrolithiasis has been reported between 1-15%, with a prevalence of approximately 5% in North America. SWL is a very common first line treatment for ureteral and renal calculi. One of its benefits is that it has few complications. However, infection remains an important complication of the procedure. Because of this risk the American Urological Association recommends pre-SWL antibiotics for all patients. However, this approach is controversial because studies to date are of poor quality and there is concern over antibiotic resistance. Therefore the European Association of Urology recommends only selective use of antibiotics pre-SWL. To resolve this conflict and establish the most appropriate strategy for Ontarians, we propose to perform a randomized trial comparing pre-procedure antibiotics to no antibiotics among patients who undergo SWL.

The primary goal of our study is to evaluate the impact of antibiotic prophylaxis on the rate of bacteriuria, symptomatic UTI, pyelonephritis and urosepsis among patients with sterile urine undergoing SWL. Our secondary goal is to determine pre-procedural characteristics that can define patient subgroups with the greatest benefit from prophylactic antibiotics.

We hypothesize that a single dose of intravenous ciprofloxacin immediately prior to SWL will decrease the relative incidence of bacteriuria, symptomatic UTI, pyelonephritis and urosepsis by 60% or greater. Additionally, we anticipate that pre-operative patient and stone characteristics such as age, gender, history of UTI, patient comorbidities, stone size, location, may be predictive risk factors that can be used to optimize patient selection for pre-operative antibiotic use.

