The lifetime risk of developing nephrolithiasis has been reported between 1-15%¹⁻³, with a prevalence of approximately 5% in North America⁴. Recent reviews suggest that the incidence and prevalence of kidney stones are increasing globally^{5,6}. Extracorporeal shock wave lithotripsy (SWL) is a preferred treatment for the majority of renal and ureteric calculi⁷⁻⁹. One significant advantage of SWL is the relatively low rate of complications. However, infectious complications are among the most common, even among patients with sterile pre-SWL urine cultures. The reported rate of bacteriuria is 8-23%^{10,11}, symptomatic urinary tract infection (UTI) is 1.4-5.7%^{12,13} and urosepsis is 0.1-2.7%^{10,11}. These reports have led to considerable interest in the use of prophylactic antibiotics prior to SWL. The American Urological Association (AUA) has recently published a Best Practice Statement on antimicrobial prophylaxis and recommended antibiotic prophylaxis for all patients undergoing SWL, even those with sterile urine. This position was based on evidence from a meta-analysis published by Pearle et al in 1997¹³. In contrast, a more recently published review by Bootsma et al.¹⁴ and a meta-analysis by Lu¹⁵ concluded that there was no role for antibiotic prophylaxis for uncomplicated patients undergoing SWL. This position is further supported by the European Association of Urology (EAU) Guidelines, which recommend selective antibiotic prophylaxis, only for patients with indwelling catheter, nephrostomy tube, or infectious stones^{16,17}.

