Since the publication of Pearle *et al.*'s meta-analysis, there have been two additional RCTs investigating the use of prophylaxis for SWL^{32,33}. Beirkens et al. attempted to perform a five arm single blinded RCT, comparing single dose ciprofloxacin 200mg IV, single dose cefuroxime 750mg IV, ciprofloxacin 200mg daily for seven days, Cefuroxime 750 mg on day one and 250 mg for six days, and placebo. A total of 177 patients were recruited (30/41/39/29/38 per group respectively). However, the study was ended after interim analysis failed to reveal any significant difference between placebo and antibiotic groups. Their results show a non-significant difference in symptomatic UTI between antibiotic and placebo groups of 2.0% vs. 3.0% at two weeks, and 1.4% vs. 2.7 % at six weeks. This study could conceivably have addressed important questions regarding the optimal regimen of prophylaxis. Unfortunately, the power of this study to find potential benefit for any given regimen is limited due to the relatively rare occurrence of UTI post-ESWL and the small sample size for the number of treatment arms. A second study by Ghazimoghaddam et al. attempted to randomize 150 patients into 3 arms (septran, nitrofurantoin, no antibiotic). The authors identified rates bacteriuria of 10-14% in each group at two weeks post-SWL and concluded that prophylaxis did not seem to be necessary. Unfortunately this study was also significantly underpowered in particular for a three arm trial³³. Our proposed study design will avoid this problem by limiting the study groups to prophylaxis

vs. placebo and we propose to recruit a sufficiently large sample size ($n \geq 661$ per arm) to detect a 60% relative decrease in incidence of infectious complication with a power of 90% and a $p=0.05$.

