The power calculation for this protocol was performed using Stata v.10.1 (StataCorp, College Station, TX). Reported incidence of bacteriuria, symptomatic UTI and pyelonephritis post-SWL vary greatly¹⁰⁻¹³. Therefore, to estimate the expected incidence of our primary outcome, we used the incidence of bacteriuria reported in the AUA Best Practice Statement on antibiotic prophylaxis¹⁷. In the AUA statement, patients undergoing SWL in the placebo arm of trials assessing antibiotic prophylaxis had a 5.7% rate of bacteriuria as compared to 2.1% among those who received prophylaxis. This represented an absolute difference of 3.6% (a 60% relative risk reduction). Therefore to achieve a power of 90% to find an absolute difference of 3.6% in the occurrence of bacteriuria, with a significance level of $p < 0.05$, 661 patients will need to be recruited in each arm for a total of 1,322 patients. Accounting for 10% loss to follow-up, the total required will be 1454, or approximately 1500 patients. Assuming that 25% of patients screened will either refuse to be randomized or will meet one of the pre-defined exclusion criteria, a total of 2000 patients will need to be screened in order to randomize 1500 patients.

Statistical analysis

Once all study data has been collected, we will report the patient characteristics at enrollment, and the primary and secondary outcomes. Comparison between RCT outcomes will be performed using Fisher's exact test for binary outcomes and Student's t-test for continuous outcomes. Lost to follow-up will be accounted for according to intent to treat analysis. Patients who are lost to follow-up will be considered not to have bacteriuria, cystitis, pyelonephritis or urosepsis and a change in IPSS of zero. This will allow us to accomplish the primary objective: to determine the impact of antibiotic prophylaxis on our primary and pre-defined secondary endpoints. We will also perform a univariate and multivariate analysis using a stepwise logistic regression model to assess predictors of our primary

outcome. This will allow us to better characterize the impact of pre-SWL antibiotic use in the context of other known risk factors for UTI.

Strengths and weaknesses of study design

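### The sample size section calls a fall from 5.7% to 2.1% a 60% reduction (it is 63.2%), so the 90% power that the Background claims at 661 per arm for a 60% decrease is about 86% to 88%

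*Combined protocol and SAP*

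**What the plan says.** The combined protocol and SAP gives the design effect in three places.

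- Section 4, Power and sample size calculation, takes its rates from a guideline statement: "patients undergoing SWL in the placebo arm of trials assessing antibiotic prophylaxis had a 5.7% rate of bacteriuria as compared to 2.1"% with prophylaxis. It then says "This represented an absolute difference of 3.6% (a 60% relative risk reduction"), and concludes that "661 patients will need to be recruited in each arm for a total of 1,322 patients" for 90% power at the 0.05 level. The power is tied there to the absolute difference of 3.6 points.
- Section 2 (Background) gives at least 661 per arm as enough "to detect a 60% relative decrease in incidence of infectious complication with a power of 90"%. It states no control rate.
- Section 1 hypothesises that ciprofloxacin lowers the incidence of bacteriuria, symptomatic UTI, "pyelonephritis and urosepsis by 60% or greater".

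The bacteriuria rate stands in for the composite: "to estimate the expected incidence of our primary outcome, we used the incidence of bacteriuria reported in the AUA Best Practice Statement". The Statistical analysis subsection plans Fisher's "exact test for binary outcomes". Recruitment continues until at least 1350 patients have complete data, which is 675 per arm.

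**The concern.** A fall from 5.7% to 2.1% is not a 60% reduction. As loose shorthand the label would do no harm, but Section 2 uses 60% as the effect the trial can detect with 90% power, and Section 1 makes 60% the smallest effect in its hypothesis. If 661 was computed for a larger effect than 60%, power at the stated target is below 90%.

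This matters most if the result is null. Section 1 says a null trial would be the best evidence so far against routine prophylaxis. Readers of such a result will ask which effect the trial had 90% power to detect, and the plan gives two answers that cannot both be true at the 5.7% control rate.

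A side issue concerns the same input. Section 4 calls the 5.7% a bacteriuria rate. In Section 2, 5.7% is the top of the range for symptomatic UTI, and for bacteriuria the text reads "The reported rate of bacteriuria is 8-23"%. The documents cannot show which label is right, and Section 4 does not say how a bacteriuria rate maps to the composite.

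**Working it through.** **Inputs.** From Section 4: control rate 5.7%, prophylaxis rate 2.1%, level 0.05, power 90%, 661 per arm, Fisher's test, and 1350 complete patients (675 per arm). From Section 2: 90% power for a 60% decrease at 661 per arm. The plan names only its software, not the formula or whether the test is two-sided. The method below is inferred because it reproduces 661.

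**1. The label.** 3.6/5.7 = 0.632, a 63.2% reduction. A 60% reduction from 5.7% gives 0.4 × 5.7% = 2.28%, a difference of 3.42 points.

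**2. Reproducing 661.** With d the difference and p̄ the mean rate, the uncorrected size per arm is

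n = [1.960·√(2p̄(1−p̄)) + 1.282·√(p₁(1−p₁) + p₂(1−p₂))]² / d².

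For 5.7% against 2.1%, p̄ = 0.039 and d = 0.036, so n = (0.53661 + 0.34935)² / 0.001296 = 605.65.

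The continuity correction gives

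n′ = (n/4)·[1 + √(1 + 4/(n·d))]² = 660.03, rounded up to **661**.

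The alternatives do not match: two-sided uncorrected 606, one-sided corrected 548, one-sided uncorrected 494.

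**3. Power at 661 per arm, same method.**

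z = [d − 1/n − 1.960·√(2p̄(1−p̄)/n)] / √[(p₁(1−p₁) + p₂(1−p₂))/n].

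- 5.7% against 2.1%: z = (0.036000 − 0.001513 − 0.020872)/0.010603 = 1.284, power 90.0%.
- 5.7% against 2.28%: z = (0.034200 − 0.001513 − 0.021101)/0.010725 = 1.080, power 86.0%.

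**4. Power of the planned test.** Two-sided Fisher power was found by summing the binomial probabilities of all tables with an exact p-value of at most 0.05.

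| Per arm | Rates | Continuity-corrected | Fisher |
|---|---|---|---|
| 661 | 5.7% vs 2.1% | 90.0% | 91.7% |
| 661 | 5.7% vs 2.28% | 86.0% | 87.7% |
| 675 | 5.7% vs 2.1% | 90.7% | 92.0% |
| 675 | 5.7% vs 2.28% | 86.8% | 88.1% |

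For scale only, 90% power for 5.7% against 2.28% needs 744 per arm continuity-corrected (743.53 rounded up) or about 716 by Fisher.

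**5. Sensitivity to the control rate, for a 60% relative reduction.** Moving up in steps of 0.1 point, the first control rate that reaches 90% power is:

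| Per arm | Fisher | Continuity-corrected |
|---|---|---|
| 675 | 6.1% | 6.3% |
| 661 | 6.2% | 6.4% |

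At an 8% control rate, Fisher power at 675 per arm is 97%. If 2.1% is held fixed instead, a 60% reduction starts from 2.1/0.4 = 5.25%, and power at 661 per arm falls to 82.7% (continuity-corrected) or 84.6% (Fisher).

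**The case against.** The strongest reply is that the operative calculation is correct. Section 4 powers the trial on the 3.6-point difference between two explicit rates, and the 60% in parentheses enters no formula. Section 2 gives no control rate, so the 86% requires carrying 5.7% over from Section 4 and reading 60% as exact. If Section 2 merely repeats the loose label, its 90% is right and only the label is wrong. All of that is fair. It confines the error to the wording and leaves the sample size alone. But 63.2% does not round to 60%, and 5.7% is the only control rate the calculation uses, so one of the two statements has to change.

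A second reply is that 86% pairs the minimum sample size with a conservative approximation. With Fisher's test at 675 per arm, power is 88.1%, only 1.9 points below the stated 90%. That is true, but the same test and size give 92.0% for 5.7% against 2.1%, so the like-for-like loss is still about 4 points. Nor do the 1500 randomised close the gap: the plan expects 10% loss, which leaves 0.9 × 1500 = 1350.

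A third reply is that the composite should be more frequent than bacteriuria alone. If 5.7% is bacteriuria, it is a floor for a composite that counts a positive culture, and a slightly higher rate restores 90% power for a 60% relative reduction. This stands and limits the practical weight of the point. The plan does not make the argument itself, however, and it sizes the trial at 5.7%.

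Finally, the two labels for 5.7% are a separate matter. The sections cite different sources, and each could report that figure. That is a request for clarification and adds nothing to the power finding.

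**Conclusion.** The concern holds. The 60% label in Section 4 is an arithmetic slip for 63.2%, and the power claim in Section 2 is wrong at the plan's own control rate. For a true 60% reduction from 5.7%, power at 661 per arm is 86.0% (continuity-corrected) or 87.7% (Fisher). The chance of missing such an effect is therefore 14% or 12%, where 10% is implied.

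This rests on a 5.7% control rate, a two-sided 0.05 level, and reading 60% as exact. The choice of formula is inferred, but the direction and the size of about 4 points are the same under Fisher's test. The 661 per arm is correct for 5.7% against 2.1%. The shortfall is modest and vanishes once the control rate reaches about 6.1% to 6.4%, depending on the method and the number per arm. It should be corrected, but it does not call the design into question.

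**What to change.** State the same target in Section 2 and in Section 4, Power and sample size calculation, and name the method. Either of these is consistent at 661 per arm:

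- a 63% relative reduction (5.7% to 2.1%), with 90% power continuity-corrected, about 92% by Fisher's exact test; or
- a 60% relative reduction (5.7% to 2.28%), with 86% power continuity-corrected, about 88% by Fisher's exact test.

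The hypothesis in Section 1 can stay as it is, since 63% lies within it.

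Add one sentence to Section 4 saying what the 5.7% measures, reconciled with the ranges in Section 2, and how it maps to the composite primary outcome. That sentence can also note that a control rate above 5.7% raises power for a 60% relative target.

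The cost is text edits in two sections. Sample size, test and timeline do not change. The only concession is that keeping the 60% wording lowers the stated power from 90% to 86%, or to about 88% if Fisher's test is the named method.

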To test this hypothesis we propose to conduct a large ($n \geq 1350$), multicenter prospective randomized, blinded, placebo controlled trial (RCT). We recognize that our primary question may be difficult to study due to low rates of symptomatic UTI post-SWL. Therefore we propose to undertake this RCT in two phases. The Vanguard phase, which will consist of up to one fourth of the total study population, will be used to determine feasibility. Feasibility will be assessed in terms of rates of patient recruitment, percent adherence to randomization, percent data completion and percent loss to follow-up. Using pre-defined criteria, if the study is deemed to be feasible without major protocol alterations, the Vanguard phase patients will be included in the larger study. Patient recruitment will then continue until our target population size has been reached. Should the Vanguard phase be unable to demonstrate feasibility, then the available data will be analyzed, which will still provide the largest and most methodologically robust dataset available in the literature at this time.

The results of our RCT, whether positive or negative, will contribute significantly to the existing literature as it will provide the strongest Level 1 evidence available for future meta-analyses and guidelines. If the study results show a benefit to antibiotic use the expected impact on patient care will be to reduce rates of infectious complications. Furthermore, our study will allow for a more selective use of antibiotics as several important predictors of infectious complications will be elucidated through a multivariate analysis. Conversely, a null study will provide the strongest evidence against routine prophylaxis in the literature to date and potentially decrease the unnecessary use of antibiotics among patients undergoing SWL. Consequently, this would represent a cost savings to the healthcare system and may reduce the risk antibiotic resistant bacteria.

2. Background, Rationale & Present State of Knowledge

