Patients routinely undergo neuroleptic anesthesia during SWL at participating centers, as such it is usual care for the patient to have a saline infusion during SWL. The choice of whether or not to administer antibiotics is usually at the discretion of the attending urologist, as there is no established standard of care. For the duration of the study, participants will be mandated to receive treatment in accord with randomization. However the attending urologist will retain the ability to break protocol in accord with their clinical judgment. Any break in protocol will be recorded as such but the data will be analyzed on an intent-to-treat basis. Ciprofloxacin was chosen as the study antibiotic as it is commonly used in everyday practice, has been used in previous RCTs on antibiotic prophylaxis pre-SWL³¹ and demonstrates a good sensitivity pattern to community acquired infections. Patients will undergo SWL with a maximum of 3000 shock waves (SW) for kidney stones and up to 4500SW for ureteric stones. Additional clinical parameters such as presence of double J, Stone characteristics and renal insufficiency will be recorded at the time of SWL by the dedicated research staff.

Patients will be asked to provide two urine samples for analysis. The first will be prior to SWL within 1 month of the procedure. On the day of procedure the patient will also complete baseline documentation. After the procedure, patients will complete follow-up documentation and a second urine culture. Urine cultures will be submitted to the laboratory or hospital most convenient for the patient at 7-14 days post-SWL and results will be forwarded to the regional site. We allow the patient to submit a urine culture at their usual laboratory in an effort to minimize the burden for the patient participating in the trial and to facilitate capture of follow-up data. This approach may be essential to capture data from patients referred from an outside institution, which may represent a significant commute. An additional advantage of this approach, in contrast to mandating the use of a central laboratory, is that it may better reflect the usual pattern of patient behavior when seeking follow-up for urinary tract symptoms post-SWL. We recognize that there may be differences in culture protocol between laboratories but we feel that these are more representative of actual practice and as such support the generalizability of the study.

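### The secondary goal asks who benefits most from antibiotics, but the planned stepwise model only identifies who gets infected

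*Combined protocol and SAP*

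**What the plan says.** Section 1 (Objectives & Specific Aims) states: "Our secondary goal is to determine pre-procedural characteristics that can define patient subgroups with the greatest benefit from prophylactic antibiotics". It lists age, gender, history of UTI, comorbidities, stone size and location as characteristics that "may be predictive risk factors that can be used to optimize patient selection for pre-operative antibiotic use". The same section says that "our study will allow for a more selective use of antibiotics as several important predictors of infectious complications will be elucidated", by means of a multivariate analysis.

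The Statistical analysis text in section 4 provides Fisher's exact test and Student's t-test for the overall arm comparisons, and then: "We will also perform a univariate and multivariate analysis using a stepwise logistic regression model to assess predictors of our primary" outcome. The stated purpose is to "better characterize the impact of pre-SWL antibiotic use in the context of other known risk factors for UTI", which suggests that treatment is in the model. Section 4 adds: "Additional clinical parameters such as presence of double J, Stone characteristics and renal insufficiency will be recorded at the time of SWL".

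Nowhere does the document name a treatment-by-covariate interaction, an arm comparison within a subgroup, an absolute benefit by level of risk, a subgroup cut-point or a rule for multiplicity.

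**The concern.** Which subgroups gain most is a question about how the treatment effect varies between patients. A main-effects model for the outcome does not address it. It gives one adjusted odds ratio for treatment, shared by everyone, and one odds ratio per characteristic for the risk of infection.

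The protocol goes straight from predictors of infection to selective antibiotic use. That step is sound if the relative effect is constant, because higher risk then means larger absolute benefit. If the relative effect differs, the group flagged as higher risk can be the group that gains less, and no planned analysis would show it. Advice on selective use could then favour the wrong patients.

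**Working it through.** **The plan's own figure.** Inputs from Power and sample size calculation: 5.7% vs 2.1%, 90% power, significance level 0.05. The two-proportion formula, two-sided, gives 606 per arm without continuity correction and 661 with it. The stated 661 is reproduced. It sizes the overall comparison only.

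**Events.** With 1,350 complete patients (675 per arm): 675 × 0.057 + 675 × 0.021 = 52.7 events.

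**Can a predictor model mislead about benefit?** Assume two equal halves with control risks of 6.5% and 4.9% (mean 5.7%). Both scenarios keep the treated mean at 2.1%. The subgroup risks and risk ratios are assumptions; the documents give none.

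| | Common risk ratio 0.368 | Differing risk ratios |
|---|---|---|
| Treated risk, higher-risk half | 2.39% | 3.5% (ratio 0.54) |
| Treated risk, lower-risk half | 1.81% | 0.7% (ratio 0.14) |
| Benefit, higher-risk half | 6.5 − 2.4 = 4.1 points | 6.5 − 3.5 = 3.0 points |
| Benefit, lower-risk half | 4.9 − 1.8 = 3.1 points | 4.9 − 0.7 = 4.2 points |
| Marker risk, arms pooled | 4.45% vs 3.35% | 5.0% vs 2.8% |
| Marker odds ratio | 1.34 | 1.83 (1.84 adjusted for treatment) |

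In the second scenario the predictor signal is stronger, yet it points to the half that gains less.

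**Precision within one half.** With 337.5 patients per arm, the standard error is √[(0.057 × 0.943 + 0.021 × 0.979) / 337.5] = 0.0148. The risk difference is 3.6 ± 1.96 × 1.48 = 3.6 ± 2.9 points, 95% CI 0.7 to 6.5.

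**Power for an interaction.** Wald test on D, the log ratio of the two odds ratios, two-sided 0.05, equal halves, N = 1,350, the same control risk in both halves:

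- SE = √Σ 1/[337.5 p(1 − p)] over the four cells; power = Φ(|D|/SE − 1.96).
- At 5.7%, ratios 0.60 vs 0.25: D = 0.896, SE = 0.641, power = Φ(1.398 − 1.96) = 29%.
- At 5.7%, ratios 0.80 vs 0.25: D = 1.195, SE = 0.624, power = Φ(1.916 − 1.96) = 48%.

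These two scenarios imply average treated risks of 2.4% and 3.0% (55 and 59 events), close to the planning rates. The planned 5.7% is a bacteriuria rate, whereas the composite also counts cystitis symptoms, so its control risk may be higher. Over an assumed range:

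| Control risk | 0.60 vs 0.25 | 0.80 vs 0.25 |
|---|---|---|
| 5.7% | 29% | 48% |
| 10% | 46% | 73% |
| 15% | 63% | 89% |
| 20% | 76% | 96% |

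**Model size and multiplicity.** Treatment, seven covariates and one interaction make nine terms: 52.7 / 9 = 5.9 events per term. Seven independent tests at 5% give 1 − 0.95⁷ = 0.30, a 30% chance of at least one false positive.

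**The case against.** The strongest reply is that the protocol means benefit in a risk-based sense. It speaks of risk factors for selecting patients and says that "several important predictors of infectious complications will be elucidated through a multivariate analysis". On that reading higher-risk patients gain more in absolute terms, the model supplies the risks, and the only defect is loose wording. This narrows the gap but does not close it: the reading needs a constant relative effect, which the plan neither states nor tests.

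The reversal example is also built to reverse, and no document gives any sign of effect modification. That is fair; it shows what is possible, not what is likely.

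The remedy would often miss that example too. The treated lower-risk half expects 337.5 × 0.007 = 2.4 events. The two risk differences differ by 1.2 points with a standard error of about 2.1, giving roughly 9% power; the odds-ratio interaction has about 39%. The marker odds ratio of 1.8 would itself reach p < 0.05 only about 54% of the time. All of this stands. It is a reason to report intervals and call the results exploratory, not a reason to leave the goal without an analysis.

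Finally, replacing stepwise selection goes somewhat beyond the missing benefit analysis. The stepwise model could remain for the separate question of predictors.

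**Conclusion.** The concern holds. Followed exactly, the stated method answers a different question from the stated secondary goal. The inference to selective use rests on an unstated and untested assumption of constant relative effect.

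The conclusion comes from the text and does not depend on the numbers. The reversal (3.0 vs 4.2 points of benefit against a marker odds ratio of 1.8) and the power figures depend on assumed subgroup sizes, risks and risk ratios, and are illustrations only. At the planning rates an interaction would be poorly estimated; it would be better estimated if the composite is more frequent than 5.7%. The primary comparison is not affected. The plan should be changed on this point before unblinding.

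**What to change.** Choose one of two routes.

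1. **Analyse benefit.**
   - For this aim, replace stepwise selection with one prespecified logistic model: treatment, age, gender, UTI history, one defined comorbidity item (for example renal insufficiency), stone size, stone location and double-J stent. Keep age and stone size continuous.
   - Add one treatment-by-covariate interaction at a time and report each with a 95% CI.
   - Report the arm risk difference with 95% CI by subgroup or by stratum of predicted risk, with cut-points fixed before unblinding.
   - Label all of it exploratory and make no significance claims.
2. **Narrow the goal.** Reword it as predictors of infection and withdraw the claim in section 1 that the results will allow more selective antibiotic use.

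The first route costs SAP wording and a few more models on data already due to be collected, with no extra patients or visits. Its drawback is wide intervals, which the SAP should state. With about 6 events per term at the planning rates, and fewer if stone location needs more than one term, one interaction at a time is the practical limit. The second route costs only wording.
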